4.3.3 Follow-Up & Outcomes

The first end point for Stage 2 is at the end of the MTM intervention. All subjects should complete the MTM intervention between Week 9 and 11; Study Days 66 and 82 (SD 74±8), barring any hospitalizations or other complications that may delay completion (see sections 4.4 and 4.5 below). The subjects will return for a second in-person visit within 2 weeks of completing intervention, between Weeks 9 and 13 (11±2 weeks); Study Days 66 and 96 (SD 81±15). At this visit, all baseline assessments will be repeated with the subject in the same order identified above (section 4.3.1). If we are conducting study procedures remotely, this visit will be conducted via phone. The EncephalApp Stroop and Liver Frailty Index will not be conducted in this circumstance. All subjects will be asked to complete the VioScreen FFQ at home within 2 weeks of completing the intervention (Weeks 9 and 13 (11±2 weeks); Study Days 66 and 96 (SD 81±15)).

Patients will then be observed for an additional 12 weeks from the date of second in-person visit. Subjects will be contacted biweekly via phone and/or email during this period to maintain contact. The main purpose of the phone calls during this time period is to maintain communication with the subject in order to prevent lost to follow-up. However, the study coordinator will also ask the subject to report their current weight. The observation period will be concluded with a phone assessment about healthcare utilization, an exit interview regarding their preferences and satisfaction with MTM (Appendix F), and the subject will also complete the ANT and SF-8. The final phone assessment represents the final end point of Stage 2 and will occur between Weeks 21 and 27 (24±3 weeks); Study Days 150 – 194 (SD 172±22).

The primary outcomes of Stage 2 are the subject retention rate at 24±3 weeks post-enrollment and the MTM intervention adherence rate at 9±2 weeks post-enrollment. Secondary outcomes measured at 24±3 weeks post-enrollment include proportion of subjects who complete all assessments and procedures, HRQOL (SF-8), cognitive function (ANT) and healthcare utilization rates and clinical outcomes. Other secondary outcomes include the proportion of subjects who complete all 24-hour Diet Recall interviews, the proportion of subjects who report improved nutritional intake and cognitive function assessed by the Encephalapp Stroop.

Table 2. Stage 2 Procedure Table

	Entry/ Day 1*	RUN-IN → BASELINE		INTERVENTION			FU 1	OBSERVATION	FU 2
		STUDY DAYS							
		11 (± 9 days)	28 (± 7 days)	32 (± 8 days)	67 (± 7 days)	74 (± 8 days)	81 (± 15 days)	81 (± 15 days) → 165 (± 15 days)	172 (± 22 days)
Informed Consent	X								
Demographics Questionnaire	X								
SF-8			X				X		X
PROMIS Self-Efficacy			X				X		
EncephalApp			X				X		
Liver Frailty Index			X				X		
Animal Naming Test			X				X		X
PROMIS Instrumental Support			X				X		
Health History Questionnaire	X								
24-hr Diet Recall		2x			2x				
VioScreen FFQ			X				X		
Phone Call/Interview				6x				6x	X
Medically Tailored Meals				X → X					
Healthcare Utilization	CHART REVIEW →								X

* Study Day 1 is defined as the calendar day on which the subject is enrolled/consented into the study.

4.4 DISTINCT CLINICAL SCENARIO: PATIENT DEATH

In the event of a subject's death during the study period we will attempt to ascertain the date and cause of death, and healthcare utilization outcome data that is available in the subject's UMHS electronic medical record.

4.5 DISTINCT CLINICAL SCENARIO: PATIENT HOSPITALIZATION

In the event of a subject's hospitalization during the study period, we will record the event as part of healthcare utilization outcome data including the number of hospital-days and the reason for

hospitalization. If the subject's hospitalization coincides with study activities, we will revise each procedure as follows:

- 1) Medically-tailored meals: If a subject is hospitalized during the MTM portion of either study stage, the study coordinator will contact PurFoods to pause future meal deliveries and ask the patient to store any meals they have at home. The subject will not be able to eat the home delivered meals during a hospitalization. Once the subject is discharged home, the study coordinator will instruct the subject to restart eating the meals they have stored at home, and will contact PurFoods to restart meal deliveries. The dates meals are stopped and restarted will be tracked.
- 2) 24-hour diet recall: If the hospitalization coincides with any of the 24-hour diet recalls, the study coordinator will contact the University of Michigan Nutrition Obesity Research Center to reschedule the assessment. The 24-hour diet recall will not be conducted while the subject is hospitalized or at a nursing facility.
- 3) In-person study visits: If the hospitalization coincides with any scheduled in-person visit, we will provide the subject an opportunity to reschedule the visit after discharge, under PI discretion.

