5.2 ADVERSE AND SERIOUS ADVERSE EVENT DEFINITIONS & REPORTING

5.2.1 Adverse and Serious Adverse Event Definitions (AE & SAE)

In the BRAINFOOD study an AE is defined as any untoward or unfavorable physical, social or psychological occurrence in a participant that can be temporally associated with the subject's participation in the study, whether or not considered directly related to the subject's participation in the research. An AE is considered an SAE if the event results in death or permanent disability and is definitely related to the subject's participation in the study. However, due to the nature of the participants enrolled and low risk nature of the treatments, the AEs and SAEs recorded and reported to the IRB will be limited using the following guidance.

Events that are not attributable to their participation in the study will not be reported as AEs, even if the data are collected for study purposes (e.g. car accident, stroke, myocardial infarction etc.). The exception to this standard is death, which will always be reported as either an AE or SAE. Additionally, expected clinical issues that subjects experience related to their ongoing medical care or chronic health problems will not be considered AEs unless it involves any of the above mentioned AE examples. Any AEs that are attributable to the study will be reported and adhere to the AE Reporting Timeline (see Table 3 below). The 4 ± 1 week (Stage 1) and 24 ± 3 week (Stage 2) end points are our final contact with subjects in which we will collect AE and SAE information. Events which qualify as AEs will be classified using the following IRB standards:

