5.3 CRITERIA OF INTERVENTION DISCONTINUATION

If the subject experiences any SAE that might be considered related to BRAINFOOD participation, the study coordinator will inform the subject to stop all intervention activities. The PI will decide whether to continue study activities thereafter. If remaining writing prompts are discontinued, every effort will be made to maintain the subject's participation in follow-up activities.

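### After a meal-related admission from which the subject recovers, section 4.5 restarts the meals at discharge home, and the stop rule in section 5.3 cannot reach the case.

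*Combined protocol and SAP*

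**What the plan says.** Section 4.5 item 1 sets the rule for meals: "If a subject is hospitalized during the MTM portion of either study stage", the coordinator pauses deliveries and asks the subject to keep whatever is at home. After discharge home, "the study coordinator will instruct the subject to restart eating the meals they have stored at home", and the supplier is asked to resume. The stop and restart dates are tracked. The item does not mention the daily protein supplements, which sections 4.2.2 and 4.3.2 schedule on the same days as the meals.

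The opening of 4.5 does capture the cause: "we will record the event as part of healthcare utilization outcome data including the number of hospital-days and the reason for" the admission. Item 3, on study visits, gives the PI a role: "we will provide the subject an opportunity to reschedule the visit after discharge, under PI discretion". Item 1 gives the PI none.

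Section 5.3 is the only written criterion for stopping the intervention. Its condition is worded "If the subject experiences any SAE that might be considered related to BRAINFOOD participation". Where that condition is met, two things follow: "the study coordinator will inform the subject to stop all intervention activities. The PI will decide whether to continue study activities thereafter". The trigger depends on section 5.2.1: "An AE is considered an SAE if the event results in death or permanent disability and is definitely related" to study participation. Section 5.2.2 has the PI rate every adverse event for relatedness and severity, and its Severe grade includes events calling for hospitalization. Section 8.3 lists allergic reactions and gastrointestinal symptoms as possible effects of the meals.

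**The concern.** For most admissions in this population, going back to the meals promptly is right. The Significance section says the meals are meant for the high-risk period after an episode of hepatic encephalopathy (HE), and an admission for HE or ascites is no reason in itself to withhold them.

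The difficulty is the admission that the meals or supplements themselves caused. There, the first question is whether the subject should be exposed again. Section 4.5 answers it by default, through the coordinator, on discharge status alone. The section that should supply an exception, 5.3, uses a trigger too narrow to do so. What is at stake is avoidable re-exposure of an individual subject to a hazard the protocol itself names. It is not bias in an estimate.

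**Working it through.** No arithmetic applies, and the plan states no figure to reproduce. The check is to follow different admissions through 5.2.1, then 5.3, then 4.5 item 1, and then to look for any other provision that governs restart.

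**The trigger.** Under 5.2.1 an event is serious only if two conditions hold together: (a) death or permanent disability, and (b) definite relation to participation. Hospitalization is not a criterion. Section 5.3 speaks of events that might be related, which suggests a wider intent. But it applies only to events already classed as serious, so the looser wording adds nothing.

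| Admission during the meal period | Serious under 5.2.1? | 5.3 triggered? | Written outcome |
|---|---|---|---|
| HE or ascites, unrelated to the meals, recovered | No | No | Restart at discharge home (sensible) |
| Reaction to the meals, fully recovered, rated definitely related and Severe | No: (a) fails | No | Restart the stored meals at discharge home |
| Reaction leaving permanent disability, rated probably related | No: (b) fails | No | Restart the stored meals at discharge home |
| Reaction leaving permanent disability, rated definitely related | Yes | Yes | Stop; the PI decides |
| Death, definitely related | Yes | Yes, but nothing is left to stop | Not applicable |

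The second row is the point at issue. For a living subject, 5.3 acts only in the fourth row.

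**Other provisions that might govern restart.**

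- Section 5.2.2: the PI rates relatedness and severity, but the section attaches no timing and no consequence for the intervention to any rating.
- Section 5.2.1: expected problems arising from ongoing care or "chronic health problems will not be considered AEs unless it involves any of the above mentioned AE examples". A reaction to study food is not such a problem. It is attributable to the study and so reportable, but reporting does not hold the meals.
- Aim 7a: withdrawal by staff or at PI discretion appears only as a category left out of the drop-out rate, with no criteria.
- Section 8.3: subjects may withdraw at any time, which leaves the initiative with the subject.
- Sections 4.2.2 and 4.3.2: the coordinator's calls include confirming that the subject is eating the meals. The Stage 2 calls also invite dietary questions. No call is required before restart.

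None of these stands between discharge home and the instruction to resume.

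**The case against.** The best defence is that 4.5 item 1 deals with logistics. It says how procedures shift when an admission coincides with study activities, and section 4.3.3 cites 4.5 only as a source of delay. Safety sits in section 5, and nothing says 4.5 overrides the PI's judgement. A sensible team would not send a subject back to food that had just put them in hospital.

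That is fair as a prediction of conduct. But the coordinator's instruction is explicit, and section 5 contains no contrary instruction for this case. The team would have to depart from the text to do the right thing.

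A second argument is that the root cause is the narrow definition of a serious adverse event. This is largely true, and it explains why 5.3 fails here. It does not remove the consequence for restart, which can be mended directly.

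Third, the supplied text lacks both the reporting timeline (Table 3) and the adverse event examples that 5.2.1 refers to. Neither is held against the plan. When the PI must rate an event therefore cannot be settled from this text. But 4.5 does not refer to the timeline, and a reporting table would be an unlikely place for a restart rule.

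Fourth, Stage 2 subjects choose their meals from a menu each week (section 4.3.2), so resumed deliveries need not repeat the offending food. This stands and narrows the concern for resumed deliveries. It does not help with meals already stored, and no weekly choice is described for Stage 1.

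Finally, requiring PI clearance before every restart would be too broad. It could delay unrelated cases in the period the meals are meant to cover. This also stands, and the change proposed here avoids it.

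**Conclusion.** The point holds for meal-related admissions from which the subject recovers without permanent disability. Followed as written, the plan tells such a subject to resume the stored meals, whatever relatedness rating the PI gives. It should be amended because the hazard is foreseen and the remedy is small.

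Its size cannot be put in numbers. The documents give no rate of meal-related admission and none is assumed. Per case, the re-exposure is to the stored meals and, less certainly in Stage 2, to resumed deliveries. The conclusion rests on reading 4.5, 5.2.1 and 5.3 literally.

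A reader might infer three stronger things that the documents do not support:

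- That the PI has no part in such an event. In fact it is an attributable adverse event that the PI must rate; what is missing is the link from that rating to restart.
- That delivery intervals measure the harm. Stage 2 deliveries come every 1 to 2 weeks within a 6-week meal period, but a share of that period would be exposure time. It would also rest on an assumed single delivery at home, so none is offered here.
- That restart at discharge is wrong in general, or that retention or adherence results would be distorted. For unrelated admissions the default is sound, and no endpoint effect has been shown.

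**What to change.** Make two linked changes.

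**Section 5.3**, add: *Any hospitalization, or any adverse event graded Severe or Life-threatening, that the PI rates possibly, probably or definitely related to the meals or supplements places both on hold until the PI decides. The PI may clear an ordinary HE or ascites admission at once.*

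**Section 4.5 item 1**, add: *The coordinator tells the PI the recorded reason for admission, during the stay where possible. At discharge home the coordinator restarts meals and supplements unless a hold under 5.3 applies.*

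Record the PI's decision beside the stop and restart dates already tracked. Unrelated admissions then restart at discharge as they do now, and the supplements are expressly covered.

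The cost is one protocol amendment, one added data field and one brief PI check per meal-period admission, using a reason and a rating scale the plan already has. The drawback is a short delay for the few subjects held. In Stage 2 this may carry some of them past the completion window of Study Days 66 to 82 (section 4.3.3), although that section already allows for delay after hospitalization.

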4.6 EARLY TERMINATION VISIT

In the event that a subject discontinues participation in the study, they will be asked to complete all final study visit assessments and questionnaires early. If they choose not to complete them, their participation will be terminated immediately. All data collection prior to termination will be retained by the study team.

4.7 SUBJECT INCENTIVES

Participants in Stage 1 will be offered a \$100 compensation for completing the trial. Participants in Stage 2 will be offered a \$200 compensation for completing the trial. Participants from both stages will be offered reimbursement for mileage driven if >50 miles driven 1-way. Mileage reimbursement will adhere to the University of maximum allowable rate for federally sponsored programs and the University of Michigan which is 57.5 cents per mile. The mileage will be calculated based on distance between the Taubman Center and the subject's home address.

5. MANAGEMENT OF ADVERSE EVENTS AND PROTOCOL DEVIATIONS

5.1 PROTOCOL DEVIATIONS

Minor protocol deviations that do not impact the safety of participants or the integrity of data must be recorded and reported to the Institutional Review Board (IRB) on an annual basis as part of standard continuing review. Major protocol deviations that may impact participant safety or the integrity of data are required to be reported to the IRB as an ORIO within 7 days of knowledge of the event.

5.1.2 Protocol Deviations may include the following items, among others:

- Enrollment despite meeting exclusion criteria
- Enrollment despite not meeting inclusion criteria
- Consent not obtained in accordance with IRB guidelines
- Baseline assessments collected outside of prescribed study window
- Baseline assessments not collected
- Outcome assessments collected outside of prescribed study window

- Outcome assessments not collected

5.2 ADVERSE AND SERIOUS ADVERSE EVENT DEFINITIONS & REPORTING

5.2.1 Adverse and Serious Adverse Event Definitions (AE & SAE)

In the BRAINFOOD study an AE is defined as any untoward or unfavorable physical, social or psychological occurrence in a participant that can be temporally associated with the subject's participation in the study, whether or not considered directly related to the subject's participation in the research. An AE is considered an SAE if the event results in death or permanent disability and is definitely related to the subject's participation in the study. However, due to the nature of the participants enrolled and low risk nature of the treatments, the AEs and SAEs recorded and reported to the IRB will be limited using the following guidance.

Events that are not attributable to their participation in the study will not be reported as AEs, even if the data are collected for study purposes (e.g. car accident, stroke, myocardial infarction etc.). The exception to this standard is death, which will always be reported as either an AE or SAE. Additionally, expected clinical issues that subjects experience related to their ongoing medical care or chronic health problems will not be considered AEs unless it involves any of the above mentioned AE examples. Any AEs that are attributable to the study will be reported and adhere to the AE Reporting Timeline (see Table 3 below). The 4 ± 1 week (Stage 1) and 24 ± 3 week (Stage 2) end points are our final contact with subjects in which we will collect AE and SAE information. Events which qualify as AEs will be classified using the following IRB standards:

5.2.2 AE Relatedness and Severity

For all AEs, the PI ([name]) will use his best judgment and indicate how related the AE is to the research procedures and intervention. He will assign the AE to one of the four categories below:

- **Definitely related:** The AE *is clearly related* to the intervention
- **Probably related:** The AE is *likely related* to the intervention
- **Possibly related:** The AE *may be related* to the intervention
- **Unlikely to be related:** The AE is *doubtfully related* to the intervention
- **Definitely not related:** The AE is *definitely not related* to the intervention

The PI will provide an AE severity:

- **Mild:** asymptomatic or mild symptoms; clinical or diagnostic observations only; no intervention indicated
- **Moderate:** minimal, local, or noninvasive intervention indicated
- **Severe:** Severe or medically significant, but not immediately life-threatening; hospitalization or prolongation of hospitalization indicated; disabling
- **Life-threatening:** Life-threatening consequences; urgent intervention indicated
- **Fatal**

The PI will AE level of expectedness:

- **Unexpected adverse events:** (i.e., has NOT been addressed or described in one or more of the following: informed consent document for this study, IRB application for this study, grant application or study agreement, protocol or procedures for this study, investigators'

brochure or equivalent (for FDA regulated drugs or devices), DSMB/DSC Reports, published literature, other documentation)

- **Expected adverse events:** (i.e., has been addressed or described in one or more of the following: informed consent document for this study, IRB application for this study, grant application or study agreement, protocol or procedures for this study, investigators' brochure or equivalent (for FDA regulated drugs or devices), DSMB/DSC Reports, published literature, other documentation, or characteristics of the study population.

5.2.3 IRBMED Reporting

AEs, SAEs, UaPs and protocol deviations will be reported to IRBMED following IRBMED reporting guidelines.

5.3 CRITERIA OF INTERVENTION DISCONTINUATION

If the subject experiences any SAE that might be considered related to BRAINFOOD participation, the study coordinator will inform the subject to stop all intervention activities. The PI will decide whether to continue study activities thereafter. If remaining writing prompts are discontinued, every effort will be made to maintain the subject's participation in follow-up activities.

6. STATISTICAL CONSIDERATIONS

6.1 SAMPLE SIZE AND ACCRUAL

The sample size for this feasibility study not driven by any hypothesis test but reflects clinical judgement. For stage 1, our prior experience suggests that 10 patients per condition is enough to detect major study barriers. For stage 2, we hope but have no way of knowing whether the intervention will impact the outcomes given its novelty. It is for that reason that we are conducting a pilot with a reasonable number of patients where outliers would not drive results.

6.2 DATA ANALYSIS

6.2.1 Quantitative Analysis

We have prespecified feasibility criteria for many outcomes on the basis of proportions and timing. All outcomes will be categorized if dichotomous and compared between groups using Fisher's exact method. All timed variables will be compared using T testing. In stage 2 we will modify the testing to account for paired values from the same individual (e.g. Paired Student's T).

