2. STUDY DESIGN

Overview: We propose a two-stage trial to determine the feasibility of MTM intervention in cirrhosis patients with a history of HE. Stage 1 will assess the feasibility of 10 different assessments and 2 weeks of MTM among three different cirrhosis populations, 1) patients with a history of \geq Grade 2 HE, 2) patients with a history of moderate to severe ascites and 3) patients with compensated cirrhosis to determine if any of the feasibility concerns are specific to particular cirrhosis complications. Patients from each group will be enrolled in equal proportion with a total of at least 30 subjects. Baseline assessments will be conducted in person at baseline and at the final study visit after completion of 2 weeks MTM intervention at 4 ± 1 weeks.

Figure 1. Stage 1 Study Design

Stage 2 is a pre-post trial after refining selection of assessments based on subject ability to complete procedures and detect changes in outcomes of Stage 1. We will enroll at least 20 subjects with a history of \geq Grade 2 HE. This stage begins with a 4 ± 1 week run-in phase with patients enrolled in person or via phone. Patients are observed in this run-in period to demonstrate interest in completing the study. Subjects will return to the clinic for a study visit in order to complete baseline assessments. Subjects in Stage 2 subjects will receive 6 weeks of MTM. During the intervention phase, subjects will receive weekly phone calls and will also be required to complete dietary recall assessments in order to measure whether they are consuming the MTM. After completion of MTM intervention, subjects will return to the clinic for an in person visit where they will repeat all baseline assessments. Thereafter, there is a 12-week observational period. Subjects will complete their final study visit and exit interview via phone between Weeks 21 and 27; Study Days 150 – 194 (SD 172 \pm 22) in order to complete final assessments.

Figure 2. Stage 2 Study Design

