4.2.3 Follow-Up and Outcomes

The end point for Stage 1 is the final in-person study visit that will occur 4 ± 1 weeks from baseline (SD 28 ± 7). At this visit, all baseline assessments will be repeated with the subject in the same order identified above (section 4.2.1), with the exception that the Demographics Questionnaire, Health History Questionnaire and VioScreen FFQ will not be conducted. We will also conduct a semi-structured exit interview to identify the participants preferences and opinions about MTM (Appendix F). If this visit must be done remotely, the study coordinator will conduct the follow-up assessments via phone. If done via phone, like the baseline outline of remote procedures, we would not be able to conduct the EncephalApp Stroop or Liver Frailty Index. Please refer to the same order of assessments for remote procedures as specified in the 4.2.1 above. The primary outcome is the subject retention rate at 4 ± 1 weeks post-baseline. Secondary outcomes include the proportion of subjects who complete all Stage 1 assessments and procedures 4 ± 1 weeks post-baseline and the proportion of subjects who complete both 24-hour Diet Recall interviews by Study Day 17. Additionally, we will measure the amount of time it takes for subjects to complete all assessments and procedures and track the recruitment and drop-out rates. A review of the experience and results from Stage 1 will

inform if changes are needed to the inclusion or exclusion criteria and schedule and quantity of assessments in Stage 2.

Table 1. Stage 1 Procedure Table

		STUDY DAY			STUDY WEEK
	Entry/ Day 1*	4 (± 1 day)	13 (± 4 days)	18 (± 1 days)	4 (SD 28 ± 7 days)
Informed Consent	X				
Demographics Questionnaire	X				
SF-8	X				X
PROMIS Self-Efficacy	X				X
EncephalApp	X				X
Liver Frailty Index	X				X
Animal Naming Test	X				X
VioScreen FFQ	X		X		X
PROMIS Instrumental Support	X				X
Health History Questionnaire	X				
24-hr Diet Recall			X		X
Motivational Phone Call/Exit Interview			X		X
Medically Tailored Meals		X → X			

* Study Day 1 is defined as the calendar day on which the subject is enrolled/consented into the study.

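### Section 6.2.1 names only a t test for Stage 1 times although Stage 1 has three groups; at 10 per group a non-significant between-group result says little about complication-specific barriers

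*Combined protocol and SAP*

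**What the plan says.** Section 2 describes three Stage 1 populations: patients with prior overt hepatic encephalopathy, patients with moderate to severe ascites, and patients with compensated cirrhosis. On allocation it says "Patients from each group will be enrolled in equal proportion with a total of at least 30 subjects". It gives the reason for three groups as "to determine if any of the feasibility concerns are specific to particular cirrhosis complications".

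Section 6.2.1 has one rule for each type of outcome. Dichotomous outcomes are "compared between groups using Fisher's exact method". For times, "All timed variables will be compared using T testing". It then says that Stage 2 testing will be modified for paired values. No alpha, contrast, three-group test or multiplicity rule is given.

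Section 6.1 bases the size on experience: "The sample size for this feasibility study not driven by any hypothesis test but reflects clinical judgement", and for Stage 1 "our prior experience suggests that 10 patients per condition is enough to detect major study barriers".

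Section 4.2.3 says that a review of Stage 1 experience and results will "inform if changes are needed to the inclusion or exclusion criteria and schedule and quantity of assessments in Stage 2".

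**The concern.** A t test compares two means, and Stage 1 has three groups. Someone following section 6.2.1 literally would have to run three pairwise t tests for each timed assessment, with nothing to control the chance of a false difference among them. The alternative is to choose a pair, and the plan does not say which.

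There is a risk in the other direction for completion and retention. With 10 patients per group, a between-group test can miss a large gap. Whether a problem is specific to one complication is the stated reason for having three groups, and section 6.2.1 is the only place that says how the groups would be compared. If a non-significant result were taken as evidence that no group has a particular difficulty, an assessment that one population struggles with could pass into Stage 2 unchanged.

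**Working it through.** **Inputs.** From the documents: three groups, 10 per group (sections 2, 3.1 and 6.1); Fisher's exact method for dichotomous outcomes and a t test for times (section 6.2.1). Assumed, because the documents give no figure: two-sided alpha 0.05, normal times with equal variance, and the completion rates shown below. The plan states no power or error rate, so there is no figure of its own to reproduce.

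**1. False differences in times.** With three pairwise tests at 0.05 and no true difference, independence would give 1 − 0.95³ = 0.143. The three pairs share groups, so the true value is lower. Simulating three groups of 10 gives 0.123, or about 12% per assessment.

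**2. Power for times.** A two-sample t test at 10 against 10 (18 degrees of freedom) has 56% power for a difference of 1.0 SD, and reaches 80% at 1.32 SD. A single one-way ANOVA across the three groups, with one group 1.0 SD away from the other two, has 58% power, and 83% at 1.32 SD. Replacing the pairwise tests by one test per assessment therefore costs no power in this setting.

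**3. What Fisher's test can show, 10 against 10.**
- 10/10 against 5/10: 2 × C(10,5)/C(20,15) = 2 × 252/15504 = 0.033.
- 10/10 against 6/10: 2 × C(10,6)/C(20,16) = 2 × 210/4845 = 0.087.
- 9/10 against 4/10: p = 0.057. 9/10 against 3/10: p = 0.020.

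So significance needs 5/10 or fewer against 10/10, or 3/10 or fewer against 9/10.

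**4. Exact power of the pairwise Fisher test.** Sum P(X = x) × P(Y ≤ critical y) over x. The main terms are:
- 95% against 60%: 0.599 × 0.367 (x = 10) + 0.315 × 0.055 (x = 9) + about 0.001 = 0.238.
- 90% against 60%: 0.349 × 0.367 + 0.387 × 0.055 + about 0.002 = 0.152.

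| Assumed completion rates | Power |
|---|---|
| 95% v 60% | 24% |
| 95% v 50% | 43% |
| 90% v 60% | 15% |
| 90% v 50% | 29% |
| 90% v 30% | 67% |

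For 80% power, the worse group must fall to about 42% if the better one is at 100%, or to about 23% if it is at 90%.

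**5. Fisher's test on the full 3×2 table.** Exact power is 27% for 90/90/60%, 47% for 90/90/50% and 85% for 90/90/30%. This is better than a single pair, but a large gap is still missed more often than found.

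**6. What 10 patients can show without a test.** The chance of seeing a barrier at least once in a group is 1 − (1 − p)¹⁰: 65% at p = 10%, 89% at 20%, 97% at 30%. Setting it to 95% gives p = 1 − 0.05^(1/10) = 0.259, about 26%.

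**7. Precision.** 9/10 completing has an exact 95% CI of 55% to 99.7%; 10/10 has 69% to 100%.

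**The case against.** The strongest reply is that section 6.1 expressly disclaims any hypothesis test as the basis of the size. A reader might infer that "10 patients per condition is enough to detect major study barriers" promises power for the tests in section 6.2.1, which they lack. The documents do not support that. The statement rests on prior experience, and read as seeing a problem at least once it is reasonable for common barriers (step 6). A 10% barrier shared by all groups would be seen among 30 patients with probability 1 − 0.9³⁰ = 96%.

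Other parts of the reply also stand:
- **Comparison by arm is inferred.** The sentence on times does not say what is compared. Aims 1a and 3a ask for results in each arm; Aim 5, on times, does not. If a within-patient comparison of baseline with Week 4 was meant, the section still needs correcting, because it introduces pairing only for Stage 2.
- **Fisher's method is not limited to two groups.** It extends to a 3×2 table, and three pairwise Fisher tests do not inflate error: simulated family-wise rates are 0.3% to 3.4% for common rates of 90% to 50%.
- **A study-wide false-positive rate is not established.** Multiplying over the nine in-person baseline assessments gives 1 − (1 − 0.123)⁹ = 69%, and a reader might conclude that false timing differences are likely. That needs all nine tested by arm and independent. With an assumed common correlation it falls to 63% at 0.3, 55% at 0.5 and 28% at 0.9.
- **No decision is tied to a p-value.** Section 4.2.3 describes a review of experience and results. That a non-significant test would be taken as clearance is a risk to guard against; the plan does not state it as a rule.

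The reply does not remove the gap in section 6.2.1: three groups, a test for two, and no contrast named.

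**Conclusion.** The point holds as a minor matter of specification. If times are compared by arm, the named test does not fit three groups, and literal use carries about a 12% chance of a false difference per assessment under the assumed alpha and normal, equal-variance times. For completion, between-group testing at 10 per group is close to uninformative except for extreme gaps: 15% to 24% power when the worse group completes at 60% and the better at 90% to 95%, these rates being assumptions. Absence of significance cannot support a conclusion that a barrier is not specific to a complication.

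It does not follow that Stage 1 is too small for its purpose, that section 6.1 is in error, or that Stage 2 decisions depend on faulty tests. For a feasibility stage with no hypothesis behind its size, the consequence is limited to how Stage 1 comparisons are run and read.

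**What to change.** In section 6.2.1:
- Report Stage 1 proportions for each group with exact 95% confidence intervals, and times for each group with a summary and 95% confidence interval.
- If a test is kept, use one three-group test per outcome in place of t tests: ANOVA or Kruskal-Wallis for times, Fisher's exact test on the 3×2 table for proportions. Label it descriptive.
- State that a non-significant result will not be taken as absence of a complication-specific barrier.

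Optionally, add to section 6.1 that 10 per condition gives a 95% chance of seeing at least once a barrier present in about 26% or more of that group.

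The cost is SAP wording and a slightly more modest stated capability. No extra patients or data are needed.
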